8.4.1.3 Correlation between MMSE and MUBADA SUVr in Clinically Normal Subjects

Spearman's correlation coefficient will be used to measure the relationship between baseline MMSE and MUBADA SUVr in clinically normal subjects. This relationship will also be presented in a scatter plot.

8.4.1.4 Correlation between FAQ and MUBADA SUVr in Clinically Normal Subjects

The same analysis as described in section 8.4.1.3 will be applied, correlating FAQ with MUBADA SUVr.

8.5 Analysis of Safety

8.5.1 Exposure

The total dose administered (MBq) of flortaucipir will be summarized in a table using descriptive statistics by imaging visits and collectively, and presented in a listing.

8.5.2 Treatment Emergent Adverse Events

A summary of TEAEs will be reported in the tables including number of all TEAEs and number of subjects who experienced at least one TEAE. The summary of TEAEs will be broken down further in descending frequency by SOC and PT, and by PT only in separate tables. A subject will be counted once if the subject reported one or more events in a given level of summarization.

All AEs will be presented in a listing.

8.5.3 Severity

TEAE severity will be reported in a table in the same manner as outlined in 8.5.2. For the summarization of TEAEs by intensity, events recorded with missing intensity will be summarized as Severe. If a subject reports the same AE more than once within an SOC/PT, the AE with the worst case severity will be summarized in the table.

8.5.4 Relationship to Flortaucipir

TEAE relationship to flortaucipir will be reported in a table in the same manner as outlined in 8.5.2. TEAEs with a missing relationship to flortaucipir will be regarded as related to flortaucipir. If a subject reports the same AE more than once within an SOC/PT, the AE most related to flortaucipir will be summarized in the table.

8.5.5 Relationship to Study Procedure

TEAE relationship to study procedure will be reported in a table in the same manner as outlined in 8.5.2. TEAEs with a missing relationship to study procedure will be regarded

as related to study procedure. If a subject reports the same AE more than once within that SOC/PT, the AE with the worst case relationship to study procedure will be used in the corresponding relationship summaries.

8.5.6 Serious Adverse Events

Serious TEAEs will be summarized in a similar manner as described in Section 8.5.2. If a subject reported more than one serious TEAE with the same SOC or PT, the TEAE will be counted only once in that SOC or PT. For the summarization of TEAEs by seriousness, events recorded with missing seriousness will be summarized as Serious.

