**7.7.4 Reporting of Serious Adverse Events**

Study site personnel must alert Eli Lilly, or its designee, of any SAE within 24 hours of their awareness of the event via a sponsor-approved method. Alerts issued via telephone are to be immediately followed with official notification on study-specific SAE forms.

Serious adverse events occurring after a subject receives a dose of study drug will be collected until 48 hours after the dosing of the study drug, regardless of the investigator's opinion of causation. Therefore, SAEs that occur later than 48 hours after the dosing of the study drug are not required to be reported unless the investigator feels the events were related to either study drug or a protocol procedure.

If a patient experiences a SAE after signing informed consent, but prior to receiving study drug, the event will NOT be reported unless the investigator feels the event may have been caused by a protocol procedure. Previously planned (prior to signing the ICF) surgeries should not be reported as SAEs unless the underlying medical condition has worsened during the course of the study.

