### 8.2 Safety Analysis

Adverse events including injection site reactions will be summarized in terms of number and percentage of subjects experiencing an AE. The summary will be further broken down by system organ class (SOC) and preferred term using Medical Dictionary for Regulatory Activities (MedDRA) terms. Adverse events will also be presented by severity, relationship to treatment and seriousness. All subjects who experience SAEs, or who discontinue due to AEs, will be summarized.

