6.6.2 Adverse Events

An AE is any undesirable experience occurring to a subject during a clinical trial, whether or not considered related to the study drug. AEs are classed by severity and seriousness.

Treatment-emergent adverse events (TEAE) are any untoward medical occurrences associated with the use of a drug in humans, whether or not considered drug related. For the purposes of this study, untoward medical occurrences will be considered associated with the use of flortaucipir, and thus be reported as TEAEs if they occur within 48 hours after administration of the PET tracer. The end of study for the purpose of AE reporting is defined as 48 hours after the administration of flortaucipir injection.

The investigator's verbatim term of both serious and non-AEs will be mapped to system organ class (SOC) and preferred terms (PT) using the Medical Dictionary for Regulatory Activities (MedDRA) Version 19.1.

Severity is classified as mild/moderate/severe (increasing severity). If a subject reports a TEAE more than once within that SOC/PT, the TEAE with the worst case severity will be used in the corresponding severity summaries.

Serious AEs (SAEs) are events that result in one of the following outcomes or constitute one of the following events:

- Death

- Initial or prolonged hospitalization (other than that required by protocol; “social hospitalization” or any hospitalization for non-medical reasons does not constitute an SAE)
- A life-threatening experience (that is, immediate risk of dying)
- Persistent or significant disability/incapacity
- Congenital anomaly/birth defect
- Considered significant by the investigator for any other reason

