8.1.2 Safety Population

The safety population will consist of all subjects who received at least one injection of flortaucipir. All baseline and safety data will be summarized and listed using the safety population. All efficacy variables described in section 6.4 will be presented in listings for the safety population.

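### The SAP's SAE, death, AE-discontinuation and procedure-relationship tables count only events 0 to 48 h after injection, so some SAEs that the protocol keeps reportable, and AE discontinuations before injection, reach no table

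*SAP*

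**What the plan says.** **Protocol.** Section 8.2 makes a commitment with no time window and no restriction to treatment-emergent events: "All subjects who experience SAEs, or who discontinue due to AEs, will be summarized". Section 7.7.4 collects every SAE up to 48 h after dosing, whatever its cause. SAEs later than that "are not required to be reported unless the investigator feels the events were related to either study drug or a protocol procedure". An SAE between consent and injection is reported only if the investigator thinks a protocol procedure may have caused it. Section 7.7.2 separates trial-emergent events (consent to injection) from treatment-emergent ones, and sets the end of AE reporting at 48 h.

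**SAP.** Under 6.6.2, events are "reported as TEAEs if they occur within 48 hours after administration of the PET tracer". Section 8.5.6 reads: "Serious TEAEs will be summarized in a similar manner as described in Section 8.5.2". Sections 8.5.7 (discontinuation) and 8.5.8 (death) follow the same pattern. So do the two relationship tables: "TEAE relationship to flortaucipir will be reported in a table in the same manner as outlined in 8.5.2" (8.5.4) and "TEAE relationship to study procedure will be reported in a table in the same manner as outlined in 8.5.2" (8.5.5). On population, 8.1.2 states "The safety population will consist of all subjects who received at least one injection of flortaucipir" and "All baseline and safety data will be summarized and listed using the safety population". Section 8.5.2 adds a listing of all AEs without naming a population.

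**The concern.** The protocol keeps certain SAEs outside the 0 to 48 h window because the investigator links them to the drug or to a study procedure. The SAP's tables then remove them on onset time alone. A procedure-relationship table that starts at injection also leaves out anything a procedure caused before injection. An AE that ends participation before the single injection is not treatment-emergent, so the discontinuation table in 8.5.7 cannot count it.

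Expanding the safety database is the study's only secondary objective. If the SAP is followed exactly, the SAE and death tables could read zero although a related SAE had been reported to the sponsor. Those are the tables most readers consult first.

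**Working it through.** The plan gives no figure to reproduce here; SAP 4.4 says that no power or sample size calculation was done. The check is a comparison of rules, followed by one illustrative calculation.

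**Step 1: the rules.**
- Reportable SAE (protocol 7.7.4): from injection to 48 h, always; after 48 h, if judged related to study drug or a protocol procedure; between consent and injection, if possibly caused by a protocol procedure.
- SAP SAE table (6.6.2, 8.1.2, 8.5.6): subject injected and onset 0 to 48 h after injection.
- SAP all-AE listing (8.5.2, read with 8.1.2): subject injected, at any onset time, provided the event is in the AE data.

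**Step 2: apply them to six fully dated SAEs.**

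| SAE | Reportable | SAE table | AE listing |
|---|---|---|---|
| Before injection, procedure-caused, never injected | yes | no | no (if 8.1.2 governs) |
| Before injection, procedure-caused, later injected | yes | no | yes |
| 24 h, any cause | yes | yes | yes |
| 60 h, drug-related | yes | no | yes |
| 60 h, procedure-related | yes | no | yes |
| 60 h, unrelated | not required | no | only if recorded |

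Five of the six are reportable, and one of those five reaches the SAE table. The same onset filter applies to the relationship, discontinuation and death tables, so the other four reach none of them. These are types of event, not expected frequencies.

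**Step 3: does another table fill the gap?** SAP 8.2 tabulates discontinuation reasons, but it defines a discontinued subject as a safety-population subject who misses the safety follow-up. A subject who leaves before injection because of an AE shows up only as a difference between the enrolled and safety counts, with no reason attached. Appendix I can class an event with a missing or partial onset date as treatment-emergent. It does nothing for a fully dated event outside the window.

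**Step 4: scale.** Assume 23 injected subjects (the count in SAP 4.4, which describes subjects dosed and with a read or quantification) and one related SAE at 60 h.
- Serious-TEAE table: 0/23 = 0%. One-sided 95% upper bound = 1 − 0.05^(1/23) = 12.2%. Exact two-sided 95% interval: 0 to 14.8%.
- Table of all reported SAEs: 1/23 = 4.3%. Exact two-sided 95% interval: 0.1 to 21.9%.

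The SAP plans no interval for AE rates; these figures only show what a reader might infer from a zero. The denominator of 23 does not apply to a subject who was never injected.

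**The case against.** The strongest reply is that SAP 8.5.2 lists all AEs. With about 23 dosed subjects, a line listing is real disclosure, so a late related SAE in an injected subject would be visible if it was entered in the AE data. That stands. A reader might infer that these events vanish from the report, and for injected subjects the documents do not support that. What remains is that protocol 8.2 promises a summary, and a listing is not one.

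For never-injected subjects the text is ambiguous. SAP 8.1.2 appears to confine safety listings to injected subjects, but the AE-listing sentence names no population, whereas the listings for medical history, pregnancy tests, ECG and follow-up contact each name the safety population. Exclusion is the likelier reading, but it is not settled.

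Three stronger readings are tempting and do not hold:
- A reader might infer that every event learned of at the follow-up call, which is never before 48 h, is wrongly left out. Protocol 7.7.2 itself ends AE reporting at 48 h, and 7.7.4 does not require unrelated later SAEs. For late onset, only related SAEs are at issue.
- A reader might work out that the call comes 96 to 120 h after a Thursday or Friday injection. That rests on one reading of the window. Protocol 5.1 says between 2 or 3 business days, 7.1.2 says within, and the fallback for non-business days also fits a calendar-day reading.
- A reader might say that the SAP denies any departure from protocol 8.2. SAP section 5 states only that study conduct did not change; it is silent on planned analyses.

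Nor do the documents show how likely a pre-injection SAE is. The only screening blood test in the visit schedule is a serum pregnancy test for women of childbearing potential.

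**Conclusion.** The conflict between protocol 8.2 and 7.7.4 on one side and SAP 8.5.5 to 8.5.8 on the other is real. Related SAEs after 48 h, procedure-caused SAEs before injection, and AE discontinuations before injection reach no table. For injected subjects these events remain in the all-AE listing; for never-injected subjects they probably do not.

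The size is one of reporting completeness. The contrast of 1/23 (4.3%) with 0/23 is illustrative. It assumes 23 injected subjects and one fully dated related SAE after 48 h. The documents report no such event, few would be expected in a study this small, and no hypothesis test or primary analysis is affected. The correction is still worth making, because the SAP as written could produce a zero that contradicts what the protocol says will be summarized.

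**What to change.** 1. Keep the TEAE tables as they are.
2. Add one summary or listing, on the enrolled population, of all reported SAEs, deaths and AEs leading to discontinuation. Show the onset period (consent to injection, 0 to 48 h, after 48 h) and relatedness to study drug and to procedure.
3. Footnote it: SAEs outside 0 to 48 h were reportable only if judged related (after 48 h, to study drug or a protocol procedure; before injection, possibly caused by a protocol procedure). All-cause events in the middle period therefore sit beside events selected for relatedness, and counts are not comparable across periods.
4. State in SAP 8.5.2 that the all-AE listing uses the enrolled population, and reconcile this with 8.1.2.
5. Do not extend the post-48 h part to non-serious AEs. Protocol 7.7.2 ends their reporting at 48 h, so such counts would be incomplete.

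The cost is SAP wording and one extra table or listing. The SAEs concerned are already reportable under the protocol, and the schedule of evaluations already collects AEs from screening, so no new data collection is needed.

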8.5.7 Adverse Events Leading to Study Discontinuation

TEAEs leading to study discontinuation will be summarized in a similar manner as described in section 8.5.2.

8.5.8 Adverse Events Leading to Death

TEAEs leading to death will be summarized in a similar manner as described in section 8.5.2.

8.5.9 Missing and Partial AE Onset Dates

See appendix 1.1 for specific algorithms to impute missing start and stop dates.

8.5.10 Follow-up Contact Data

The follow-up contact information captured on the CRF will be presented in a listing for the safety population.

APPENDIX I: ALGORITHMS TO HANDLE MISSING AND PARTIAL DATES

1.1.MISSING AND PARTIAL AE ONSET AND END DATES

If the AE onset dates are missing, then the most conservative approach will be used to decide if the AE is TEAE or not, as detailed in the table below:

AE ONSET DATE/TIME	AE STOP DATE/TIME	ACTION
Partial, but known components show that it cannot be on or after an injection date/time and within 48 hours post-injection	Known	Not TEAE
	Partial	Not TEAE
	Missing	Not TEAE
Partial, could be on or after an injection date/time and within 48 hours post-injection	Known	If stop date/time < flortaucipir injection date/time, then not TEAE If stop date/time >= flortaucipir injection date/time, then TEAE
	Partial	Impute stop date as latest possible date (i.e. 59 if minutes unknown or 23:59 if hours and minutes unknown; last day of month if day unknown or 31st December if day and month unknown), then: If stop date/time < flortaucipir injection date/time, then not TEAE If stop date/time >= flortaucipir injection date/time, then TEAE
	Missing	Assumed TEAE
Missing	Known	If stop date/time < flortaucipir injection date/time, then not TEAE If stop date/time >= flortaucipir injection date/time, then TEAE
	Partial	Impute stop date as latest possible date (i.e. 59 if minutes unknown or 23:59 if hours and minutes unknown; last day of month if day unknown or

AE ONSET DATE/TIME	AE STOP DATE/TIME	ACTION
		31st December if day and month unknown), then: If stop date/time < flortaucipir injection date/time, then not TEAE If stop date/time >= flortaucipir injection date/time, then TEAE
	Missing	Assumed TEAE

Leo Document ID = b9e6f9ff-92af-4092-bb6e-571c13a139ff

Approver: [REDACTED]
Approval Date & Time: 14-Mar-2019 17:30:12 GMT
Signature meaning: Approved

Approver: [REDACTED]
Approval Date & Time: 14-Mar-2019 18:18:43 GMT
Signature meaning: Approved

Approver: [REDACTED]
Approval Date & Time: 14-Mar-2019 18:23:12 GMT
Signature meaning: Approved

Approver: [REDACTED]
Approval Date & Time: 14-Mar-2019 19:08:13 GMT
Signature meaning: Approved
